The Surgical Care Improvement Project (SCIP) also used audit-and-feedback to improve antimicrobial-prescribing among surgical inpatients. SCIP was a nationwide initiative to reduce surgical complications through accountability and public disclosure. Ambulatory surgeries and urologic procedures were not included in SCIP. Compliance with SCIP standard 3, the discontinuation of antimicrobials within 24 hours of the operation, increased from <60% at baseline to 94% in 2012.¹³ These improvements were achieved even before CMS tied SCIP measures to hospital reimbursements in fiscal year 2013.

Although audit-and-feedback has been effective in improving antimicrobial-prescribing among certain types of surgical specialties, its benefit among urologic providers is unclear. In 2015, urologists accounted for the 8th highest number of outpatient antimicrobial prescriptions among all specialties.¹⁴ Given such a high frequency of antimicrobial-prescribing, there may be opportunities for enhanced antimicrobial stewardship among urologists.

The Best Practice Policy Statement on Urologic Surgery Antimicrobial Prophylaxis, published by the American Urological Association (AUA), recommends single-dose antimicrobial prophylaxis without post-procedural continuation is recommended for most urologic procedures.¹⁵

However, the unnecessary use of post-procedural antimicrobials is common after urologic procedures, according to administrative data our group analyzed from the VHA. In a national

cohort of nearly 30,000 patients, extended post-procedural antimicrobials (defined as >24 hours) were prescribed after 37.2% of urologic procedures for a median duration of 3.0 excess days.⁵ Based on a manual chart validation, 177 of 211 (83.9%) patients who received excessive post-procedural antimicrobials (i.e. more than 24 hours after the procedure) did not have a clear indication for antimicrobial therapy. At the hospital-level, the use of excessive post-procedural antimicrobials varied widely. For example, after transurethral resection of bladder tumors, the median frequency of excessive post-procedural antimicrobial-prescribing at the hospital-level was 27.9% with an interquartile range of 14.7-55.0%. Overall, we estimate that there are 30,000 days of unnecessary antimicrobial therapy per year in VHA patients undergoing these three urologic procedures.

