- Delivery method: At baseline, feedback will be given via a video-conferencing call in which we show the team their feedback report and explain what it means. All subsequent feedback will be delivered through e-mail.
- Unit of delivery: The feedback will be given to all practicing urologists at a site.
- Deliverer: The baseline video-conferencing call will be attended by the study team (Drs. [name], [name] and [name]). The electronic feedback will be sent from the PI's e-mail account.
- Setting: The intervention will be delivered via video-conferencing (baseline) or via e-mail (months 1, 3, 5, 7, 9, and 11).
- Exposure quantity and duration: Feedback will be given at baseline and every 2 months
- Time span: 12 months
- Activities to increase compliance or adherence: During the introductory call, the study team will review the AUA's guidelines on antimicrobial prophylaxis and the potential harms of extending antimicrobial prophylaxis beyond a single dose.^{15,18} The Chief of Urology at each site will be encouraged to be a local champion for more judicious use of post-procedural antibiotics.

Objectives:

- Study objectives: Evaluate whether a pilot audit-and-feedback intervention across 3 hospitals can safely reduce the unnecessary use of post-procedural antimicrobials in patients undergoing urologic procedures.
- Hypotheses: An bundled intervention across 3 hospitals will facilitate safe reductions in post-procedural antimicrobial-prescribing.

Outcomes:

Clinical outcomes are listed below. Data for all clinical outcomes will be extracted from the Corporate Data Warehouse (CDW) using the VA Informatics and Computing Infrastructure (VINCI).

Primary outcome

Excess post-procedural antimicrobial use is defined as a prescription for a designated antimicrobial agent on post-procedural day one. Designated antimicrobials will be antimicrobial agents potentially used for a urinary tract-related indication, as outlined in our prior work.⁵ This definition will be used to minimize the chance of including patients receiving antimicrobials for non-urologic or non-prophylactic indications.

Patients will be eligible for this outcome if they underwent a medical procedure coded with a Current Procedural Terminology (CPT) code or an International Classification of Diseases, 10th version, Procedure Coding System (ICD-10-PCS) code for TURPs, TURBTs, and URSs during

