the 2-year baseline period or during the 1-year intervention period. These three procedures were selected because they are all common procedures performed endoscopically with no skin incision required. In addition, for all 3 procedures, the AUA guidelines give a clear recommendation for giving a single dose of antimicrobial prophylaxis.¹⁵

Secondary outcomes

Excess post-procedural antimicrobial duration is defined as the duration of continuous excessive post-procedural antimicrobial use, as quantified as days of therapy per National Healthcare Safety Network methodology.¹⁹

Safety outcomes

- Late antimicrobial prescription is defined as the prescription of a designated antimicrobial that does not qualify as a post-procedural antimicrobial (see above) by any provider within 7-30 days of the date of the patient's urologic procedure. All late antimicrobial prescriptions must be agents potentially used for a urinary tract-related indication, as outlined in our prior work.⁵
- Return visits: seeking care in an Emergency Department, Urgent Care Clinic or hospital readmission to an acute-care bed at a VHA facility for any indication within 30 days of the patient's index urologic procedure.

Assignment Method: Intervention sites will be selected from the top tertile of all sites, as ranked on the frequency of excess post-procedural antimicrobial-prescribing. Eligible new sites will be invited until 3 unique sites agree to participate.

Sample Size: This was a pilot trial, so no sample size calculation was performed.

Blinding: None

Unit of Analysis: Each medical center (3 intervention)

Statistical Methods:

Patient demographics, comorbidities, and types of procedures are presented by count and percentages. Observations occurring within the implementation phase (July 2022) were omitted from all analyses. Observations from each of the three sites were stratified into three data sets to accommodate separate analyses on each site.

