To model the primary outcome, we used a logistic regression model and a set of three explanatory variables: time, a binary indicator for an observation occurring within the intervention phase, and an interaction term between these two main effects (time and intervention). Time was measured in days divided by 365, giving an annualized figure for the time coefficient estimate and interaction coefficient. In the tables of results of these logistic regression models, the coefficient estimates are exponentiated to display estimated multiplicative effect on the odds; 95% confidence intervals are also provided on the odds scale. The median duration of post-procedural antimicrobial prescriptions at each site were compared using the Wilcoxon rank-sum test.

To model the secondary outcomes, we used a similar approach to what is described above with the addition of a fourth explanatory variable (a binary indicator for the primary outcome) to the

logistic regression model. This last variables was included to assess the risk of these secondary outcomes in patients who were not exposed to post-procedural antimicrobials compared to those who were exposed.

References:

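### The safety models compare patients with and without day-one antimicrobials with no patient-level adjustment, so withholding can look protective when it has no effect, or neutral when it is harmful

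*Combined protocol and SAP*

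**What the plan says.** Statistical Methods specifies a logistic model with "a set of three explanatory variables: time, a binary indicator for an observation occurring within the intervention phase" and the product of the two. For the secondary outcomes it adds the primary-outcome indicator, that is, whether the patient had a designated antimicrobial on day one. The purpose is stated: the term was "included to assess the risk of these secondary outcomes in patients who were not exposed to post-procedural antimicrobials" relative to exposed patients. The only outcome listed under the Secondary heading is duration, which does not suit a logistic model, so I take this passage to cover the two safety outcomes: late prescription and return visit.

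No patient-level variable enters any model. "Patient demographics, comorbidities, and types of procedures are presented by count and percentages", and nothing more is done with them. Fitting is by site: "Observations from each of the three sites were stratified into three data sets".

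Two other places bear on the point. The Background reports a chart validation in which "177 of 211 (83.9%) patients who received excessive post-procedural antimicrobials" "did not have a clear indication for antimicrobial therapy". The Primary outcome section limits the outcome to agents with a possible urinary use and explains: "This definition will be used to minimize the chance of including patients receiving antimicrobials for non-urologic or non-prophylactic indications".

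**The concern.** Patients were not allocated to antimicrobials; a urologist chose. Some exposed patients may have been treated because of a sign of infection or a complication, and that sign may itself predict a return visit or another urinary antimicrobial. The exposure coefficient would then mix any effect of the drug with the higher risk of those patients. Fitting each site separately removes differences between sites, but not the selection of patients within a site.

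The agent list is the plan's only guard. It can screen out treatment of non-urinary conditions. It cannot separate prophylaxis from treatment of a urinary infection, because both use the listed drugs. Late prescription is defined on the same kind of agent, so one urinary problem could drive both exposure and outcome.

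Safety is part of the stated objective and hypothesis, and the Background says the results could inform a wider programme. A contrast that can show withholding as protective under a true null, or can cancel a real harm, should not be read as evidence of safety.

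**Working it through.** **1. The plan's own figure.** 177/211 = 0.839, which reproduces the stated 83.9%. The remainder is 34/211 = 0.161.

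**2. Assumptions not in the documents.** Antimicrobials have no effect on the outcome. Event risk is 10% without an indication and 25% with one (range 20-30%). All indicated patients are exposed. Exposure falls from 60% to 25%, and only unindicated use is lost. The 16.1% is carried over from the earlier cohort.

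**3. Baseline odds ratio, exposed versus unexposed.**
- Exposed risk = 0.161 × 0.25 + 0.839 × 0.10 = 0.124; unexposed risk = 0.10.
- OR = (0.1242/0.8758)/(0.10/0.90) = 1.28. With 20% and 30% in place of 25% it is 1.18 and 1.37.
- If 5% of unexposed patients are also indicated, their risk is 0.05 × 0.25 + 0.95 × 0.10 = 0.1075 and the OR is 1.18. If 10% are, their risk is 0.115 and the OR is 1.09.

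**4. Intervention phase.** Indicated patients are 0.60 × 0.161 = 9.7% of all patients, hence 9.7/25 = 38.7% of the exposed. Exposed risk = 0.387 × 0.25 + 0.613 × 0.10 = 0.158.

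**5. The single coefficient the plan estimates.** Take the minimum volume of 75 procedures a year: 150 at baseline and 75 in the intervention year, 225 in all.

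| Phase | Group | Patients | Expected events |
|---|---|---|---|
| Baseline | exposed | 90 | 11.18 |
| Baseline | unexposed | 60 | 6.00 |
| Intervention | exposed | 18.75 | 2.96 |
| Intervention | unexposed | 56.25 | 5.63 |

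A logistic fit to these counts with phase and exposure gives OR 1.40 (1.26-1.54 over the 20-30% range). A Mantel-Haenszel check by hand gives (4.02 + 2.00)/(3.15 + 1.18) = 1.39. Read as unexposed versus exposed, the 1.40 is 0.72 (0.65-0.79). The true value is 1.00.

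**6. Precision.** The standard error of the log OR at 225 patients is about 0.447. The 95% interval is exp(0.334 ± 1.96 × 0.447) = 0.58 to 3.36.

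**7. Masked harm.** At baseline, with no indicated unexposed patients, a true withholding OR of 1.28 (1.18-1.37) would be cancelled exactly and appear as 1.00.

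**8. Simulation of the planned four-term model.** This used 10% base risk, exposure of 55% before and 35% after, and 600 replicates per setting. Under a true null the 95% interval lay wholly on the side of withholding being protective in 6%, 10% and 21% of runs at 225, 600 and 1,500 patients, when indicated patients had twice the risk. With three times the risk it was 13%, 30% and 59%. The nominal rate is 2.5%. With a true withholding OR of 1.25 and three times the risk, the model returned 0.87-0.90. Adding a perfect indicator of the reason brought the null estimate back to 0.99-1.05.

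**9. Before/after comparison without the exposure term.** Overall risk at baseline is 0.60 × 0.1242 + 0.40 × 0.10 = 0.1145. In the intervention phase it is 0.25 × 0.1580 + 0.75 × 0.10 = 0.1145. The comparison correctly shows no change. With the exposure term included, the fit in step 5 gives a phase OR of 1.13, because the phase OR is 1.00 among unexposed patients but (0.1580/0.8420)/(0.1242/0.8758) = 1.32 among exposed patients.

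**The case against.** The case for the plan has real substance. Most treated patients in the chart validation had no clear indication, so a reader who infers that exposed patients in general were treated for a reason goes beyond the documents. The 16.1% comes from a national cohort defined by use beyond 24 hours, whereas this trial uses day-one prescribing at three sites from the highest tertile of use. If those sites prescribe more by routine, the indicated share and the bias could be smaller. Any indicated patients left untreated would also shrink it, as step 3 shows.

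Three stronger readings are tempting and are not supported:
- **That the bias grows as the intervention succeeds.** In the illustration the intervention phase alone gives OR 1.69, but that requires feedback to remove only unindicated use. It is also not what a coefficient spanning both phases estimates.
- **That the plan rests its safety conclusion on this coefficient, or chose it to favour one answer.** The documents say neither, and the phase and interaction terms are in the same model.
- **That the error is to make withholding look safe when it has no effect.** If it has no effect, it is safe. The error is apparent protection under the null, or hidden harm.

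At about 225 patients, one site would seldom give a convincing protective result from this bias alone. Other selection, for example by procedure type, could add to the bias or offset it.

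What remains is that the contrast is the stated purpose of the term, it has no adjustment, restriction or caution, and the agent list does not close the gap. Low precision is acceptable in a pilot, but it does not cure a directional bias.

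**Conclusion.** The point holds in limited form. The exposure odds ratio in the safety models is an unadjusted, non-randomised contrast open to confounding by indication, and it should not be read as evidence on the safety of withholding. Under the assumptions listed, a true OR of 1.00 would appear as about 1.40 (1.26-1.54), exposed versus unexposed. The baseline-only figure is 1.28, or 1.18 and 1.09 if 5% or 10% of unexposed patients are also indicated. The size rests on risks and exposure levels that the documents do not give and on a borrowed 16.1%. The direction is likely rather than certain, and the interval at a minimum-volume site would be wide.

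**What to change.** 1. Base the safety statement on the before/after comparison, fitted without the exposure term. Exposure lies between the intervention and the outcome, and step 9 shows that including it distorts the phase estimate.
2. If the exposure contrast is kept, adjust for procedure type, age and one summary of the comorbidities already extracted. Fit one model across the three sites with site as a fixed effect. One site of 225 patients would have about 26 events in the illustration, too few for extra covariates on top of the existing four terms; three such sites give about 77. If the warehouse fields are available, exclude patients with a positive urine culture or a coded urinary infection up to the procedure day.
3. Report the result as an adjusted association with residual confounding by indication. Signs that first appear on day one are not captured, so the near-perfect recovery in step 8 should not be expected.

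The cost is some extra extraction and analysis, fewer patients and a wider interval for this contrast, and the assumption of a common exposure odds ratio across sites. The methods are written in the past tense in a document dated March 2024, after a July 2022 implementation phase. The change would therefore probably be a reanalysis, and should be labelled post hoc.
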